[USE THIS BIOMEDICAL PROTOCOL TEMPLATE IF YOUR PROJECT INVOLVES ANY PHYSICAL CONTACT OR MEDICAL INTERVENTIONS WITH PARTICIPANTS]

INSTRUCTIONS:

- Depending on the nature of your research, some sections may not be applicable to your research. These sections can be removed as needed.
- When you write a protocol, keep an electronic copy. You will need to modify this copy when making changes.

PROTOCOL TITLE:

Treatment of Stress-Related Psychopathology: Targeting Maladaptive and Adaptive Event Processing

PRINCIPAL INVESTIGATOR:

*[name]
Psychological Sciences
[contact]
[contact]*

UH FACULTY ADVISOR:

If the principal investigator's primary role at UH is resident, fellow or student, identify a faculty advisor.

N/A

OTHER DEPARTMENTS INVOLVED IN THIS STUDY (IF APPLICABLE):

N/A

VERSION NUMBER:

Include the version number of this protocol if assigned by an outside entity.

N/A

DATE:

12/14/2021

Objectives

Directions: Describe the purpose, specific aims or objectives. Be sure to also include the hypothesis being tested

Positive Processes and Transition to Health (PATH) includes six, 90-min sessions that target maladaptive event processing (unproductive processing, avoidance, and impaired reward sensitivity), while also promoting parallel adaptive event processing (constructive processing, approach, and reward seeking) for destabilizing life events and for positive events. PATH uses a platform of narrative revisiting of destabilizing life events, as well as positive life event reminiscence. Patients will be selected for having experienced a destabilizing life stressor and related psychopathology. The R61 trial ($N = 45$) will examine whether PATH engages the therapeutic targets, with clear Go/No Go rules. In the R33, patients ($N = 135$) will be randomized to PATH or progressive muscle relaxation (PMR) and assessed over a 3-month follow-up.

The Specific Aims are:

Specific Aim 1: Engage Therapeutic Targets (R61): In an open trial ($N = 45$), we will examine whether PATH changes therapeutic targets (unproductive processing, avoidance, impaired reward processing) from pre- to 3-month follow-up, with at least medium effects ($d = 0.60$) on two of three primary target measures and at least ($d = 0.50$) on one secondary target measure. We will examine dosing and timing of effects.

Specific Aim 2: Replication of Target Engagement (R33): In a randomized control trial ($N = 135$), we will examine whether PATH alters therapeutic targets from pre- to 3-month follow-up in comparison to PMR.

Specific Aim 3: Link Changes in Targets to Changes in Stressor-related Outcomes (R33): We will examine whether changes in therapeutic targets (pre- to post-) predict improvement in PTSD and depression symptoms (pre- to 3-month follow-up).

Specific Aim 4: Feasibility and Dropout/Acceptability of PATH (R61/R33): We will examine whether patients perceive PATH as helpful and complete/adhere to treatment, and therapist fidelity.

There is an urgent need to develop novel treatments, given the prevalence, impact, and cost of PTSD and MDD (e.g., Hoge & Chard, 2018). PATH is an innovative intervention that targets three interrelated, transdiagnostic processes that maintain stressor-related psychopathology. PATH's unique early and sustained focus on positive emotions could improve adherence and outcome, particularly in those with the reward deficits commonly seen in PTSD and MDD. Further, PATH's focus on positive emotions and "stuck" processing targets unique processes largely absent in current PTSD therapeutics. PATH is novel in applying exposure principles to depression, not just PTSD. This brief, positive, mechanistically precise, transdiagnostic treatment has the potential to improve treatment engagement and outcomes, identify clear therapeutic targets that predict better outcomes, and ultimately reduce the costly burden of stressor-related psychopathology.

We hypothesize that (1) those in PATH will have significant changes in the therapeutic targets, (2) those in PATH will show a greater change in therapeutic targets than those receiving Progressive Muscle Relaxation (PMR), (3) changes in therapeutic targets predict improvement in PTSD and depression symptoms, and (4) those in PATH will perceive the intervention as helpful and adhere to treatment.

Background

Directions: Describe the relevant prior experience and gaps in current knowledge describing how it will add to existing knowledge. Include any relevant preliminary data.

Novel, more effective, efficient, tolerable, transdiagnostic interventions are needed. Posttraumatic stress disorder (PTSD) and depression (MDD) frequently co-occur (more than 60%; Rytwinski, Scur, [name], & Youngstrom, 2013), with shared distress-related symptoms and substantial impairment and disease burden (Post, [name], et al., 2011; WHO, 2004). State-of-the-art psychotherapies for PTSD and MDD show clinically meaningful gains (Cuijpers et al., 2014; Watts et al., 2013). Yet, there is substantial room for improvement, given considerable dropout rates, time-intensive and emotionally taxing interventions, and a significant minority left with debilitating symptoms and risk for relapse. Emerging models of psychopathology (e.g., [name] et al., 2015; McNally, 2016) propose that negative and positive feedback loops create vicious cycles that increase the risk of getting “stuck” in pathological states (e.g., Holtzheimer & Mayberg, 2011; van de Leemput et al., 2014). Accordingly, next-wave psychotherapies must target key maladaptive processes and facilitate transition to more adaptive ones (Hofmann & [name], 2019). Therapies following stressful life events focus almost exclusively on negative emotion, which may contribute to dropout. Capitalizing on positive emotions early may make treatment less daunting and harness the power of the positive affect system.

Exposure to destabilizing life events (e.g., sudden loss of loved one, sexual assault, job loss) ranges from 50-89.5% in the U.S. population (Kessler, 1995; Kilpatrick et al., 2013). There is compelling support for the etiological role of such stressful life events for a range of psychopathology (Harkness & Monroe, 2016), including persistent problems in the negative and positive valence systems related to PTSD and MDD. Decades of research have isolated central maladaptive and adaptive processes linked to psychopathology and resilience following destabilizing life events (Aldao et al., 2010; [name] et al., 2015; Waugh & Koster, 2015). These therapeutic targets include: **unproductive/constructive event processing** (e.g., rumination vs. updating with corrective information, meaning-making); **avoidance/approach** (e.g., disengagement vs. engagement); and **impaired reward sensitivity/positive emotion engagement** (e.g., impaired reward processing vs. reward seeking). Together, these maladaptive processes are hypothesized to form a “stuck” system that prolongs negative mood, interferes with adaptive event processing, and increases reactivity to future stressful events, whereas their adaptive counterparts disrupt this system and promote resilience.

Positive Processing and Transition to Health (PATH)

PATH targets three transdiagnostic maladaptive processes and facilitates their more adaptive counterparts: 1) unproductive and constructive processing, 2) avoidance and approach, and 3) impaired reward sensitivity and positive emotional engagement and reward seeking. PATH is designed for individuals who have stressor-related psychopathology and can treat symptoms of PTSD or depression or the combination.

Inclusion and Exclusion Criteria

Describe how individuals will be screened for eligibility. Using the tables below, describe the inclusion and exclusion criteria that will define who will be included and excluded in your final study sample.

Inclusion Criteria

1. Destabilizing life event involving profound loss or threat, with a minimum duration of 12 weeks since the event.
2. Between the ages of 18 and 65.
3. Elevated target: Scores of at least moderate (1 or higher) on at least 2 of the 3 target mechanisms: re-experiencing or ruminative processing of the destabilizing event (PSS-I items: 1, 2, 3, 4 or QIDS-C item 11), avoidance (PSS-I items 6, 7, 8), or reward deficits (PSS-I items 12, 13, or QIDS-C item 13)
4. Elevated symptoms on either the PSS-I or QIDS-C (at least moderate): 18 on PSS-I (Foa et al., 2016) and/or 11 on QIDS (moderate depression severity; Rush et al., 2003), with symptoms persisting for 1 month or longer.

Exclusion Criteria

1. Current diagnosis of psychotic, bipolar, or substance use disorder.
2. Severe self-injurious behavior or suicide attempt within the prior 3 months.
3. Unwilling or unable to discontinue current CBT or unstable dose of psychotropic medications within prior 3 months.
4. Ongoing intimate relationship with the perpetrator (in assault-related event).
5. No clear memory of event or occurred more than 5 years ago.
6. Residence outside of the states of Ohio, Delaware, or Washington

Number of Research Participants

Directions: Indicate the maximum number of research participants to be accrued locally, and, if this is a multi-site study, indicate the maximum number of research participants to be accrued across all sites.

This study is being conducted in collaboration with the University of Washington and the University of Delaware. In total, for the R61, 45 participants will be evenly accrued across all sites, and for the R33, 135 participants will be evenly accrued across all sites.

Recruitment Methods

Describe how subjects will be identified (the source of potential research participants), and also how, when, and where they will be recruited. Describe all methods of contact / communication.

We will emphasize online advertising (e.g., Craigslist and study website, pathway2help.com). We will increase our visibility in the community by boosting awareness of our programs and ongoing research. This includes routine postings on free advertising websites (e.g., Craigslist and study website). We expect that the bulk of our study participants will come from online advertisement.

In addition to online advertising, we will also send letters describing the study to healthcare providers who can bring this study to the attention to their patients who may be eligible. We will also send these providers brochures that they can distribute to interested patients. These brochures contain a site-specific phone number and a link to the study website so that interested participants can contact the study team to learn more about this project. Finally, we will also post paper flyers for the study throughout the

community, such as on college campuses, churches, grocery stores, libraries, etc.

Setting

Directions: Make sure to describe:

- 1) *The sites and locations where your research team will conduct the research.*
- 2) *Where your research team will identify and recruit potential research participants, and*
- 3) *Include the physical location where research procedures will be performed.*

Adults will be recruited from the Cleveland, OH area. Interviewers will collect demographic data and complete an eligibility screening form (type of destabilizing event, inclusion/exclusion criteria) via phone screens. Potentially eligible individuals will be scheduled for an intake and complete informed consent in-person before doing an assessment; those excluded will be given referrals. All assessments and intervention sessions will take place in the Mather Memorial building at Case Western Reserve University, in Room 137. (However, see below for COVID-19 changes to the study setting.) Adults will also be recruited from Wilmington/Newark, DE (University of Delaware) and Seattle, WA (University of Washington).

COVID-19 Changes

For the foreseeable future, due to the COVID-19 pandemic and current restrictions on in-person research across all three sites, all study procedures will take place remotely and online, rather than in-person. Specifically, the different procedures are as follows:

- Participants will be recruited from across states instead of across cities. That means adults can reside anywhere in Ohio, Delaware, and Washington, instead of just the Cleveland, Wilmington/Newark, and Seattle areas.
- Intakes will occur via the secure videoconferencing platform Zoom.us (HIPAA compliant and currently used by the University Counseling Center), rather than in-person. Participants will review and sign informed consent forms via REDCap, while the assessor is on Zoom with them.
- The participants will receive the PATH intervention through Zoom rather than in-person.
- For participants without technology to complete the measures, a member of the study team will drop or mail the Kindles off at their home in sealed envelope and receive them after subjects complete all study procedures.

There is a potential we will go back to in-person procedures in the future (i.e., when restrictions are lifted), should we reach that point, we will modify the protocol to reflect this change.

Consent Process

Describe if the study will be obtaining consent, or if the study will be applying for a waiver of consent.

Potentially eligible individuals will complete their informed consent in-person before starting intake (see below for COVID-19 changes). Participants will be informed that participation is optional and that they may discontinue participation at any time. Participants will be provided with the contact information for study staff and the Human Subjects division.

COVID-19 CHANGES

Potentially eligible individuals will complete their informed consent via REDCap, while an assessor is on Zoom with them. Assessors will provide participants with the same information as above. Consent forms have been uploaded that reflect changes to an online and remote intervention and assessments. Assessors will also ask about collecting emergency contact information, in case it's ever needed.

Sharing of Results with Research Participants

Directions: Describe whether results (study results or individual subject results such as results of investigational diagnostic tests, genetic tests, or incidental findings) will be shared with the research participants or others (e.g. the subject's primary care physicians) and if so, describe how the results will be shared.

- Results will not be shared with research participants
- Results will not be shared with research participants' doctors

Study Design

Directions: Describe and explain the overall study design. (eg: single visit, single-blind, double-blind, non-randomized, randomized, blood draw, investigational drug, device etc.)

[figure not shown]
Open Trial of PATH: Engage the Targets (R61)

The R61 will be an open trial to determine if Positive Processes and Transition to Health (PATH) engages the proposed targets: unproductive processing, avoidance, and reward deficits in a *sample of 45 adults* who have experienced a destabilizing life event involving profound loss or threat, report persistent stressor-related symptoms of PTSD and/or depression, and are elevated on symptoms related to 2 of the 3 therapeutic targets. Patients will receive six 90 minute sessions of PATH (with 2 boosters, if partial responders). Primary targets will be assessed at pre-treatment, week 3, post-treatment, and at 1- and 3-month follow-up; secondary targets at pre-treatment, weekly during treatment, post-treatment, and at 1- and 3-month follow-ups. If GO criteria are achieved (Table 3), we will proceed to the R33.

RCT of PATH: Target Engagement and Link to Clinical Outcomes (R33)

The R33 will examine target engagement (unproductive processing, avoidance, and reward deficits) and whether change in PATH targets predict functional outcomes (PTSD, depression). The sample will be 135 adults who have experienced a destabilizing life event and report persistent stressor-related symptoms (Table 1). Patients will be randomized to PATH or progressive muscle relaxation (PMR; six 90 minute sessions) and assessed on the same schedule as in the R61. See Figure 2 for study design.

Figure 2. Study Design R33

Study Procedures

Directions: 1) Provide a description of all study-related research procedures being performed 2) include procedures being performed to monitor research participants for safety or minimize risks 3) include all drugs and/or devices used in the research and the purpose of their use and their regulatory approval status 4) describe the source records including medical or educational records, which will be used to collect data about subjects.

Session 1 (Overview) provides the PATH rationale and a review of life events (PATH of life: negative and positive). Therapists explain that unproductive processing, avoidance, and reward deficits work together to prolong distress and will be the targets of PATH. Therapists describe parallel processes of constructive processing, approach, and positive emotional engagement that help one to move forward and make meaning. In line with this, a rationale for an explicit focus on positive events/emotions will be provided.

Sessions 2-4 focus on a verbal narrative of the destabilizing life event (revisiting negative event and processing as is done in imaginal exposure), reminiscence and processing of a major positive life event, and real-life practice to enact what was taught. In positive reminiscence, clients vividly remember the positive event providing details and focus on positive emotions. Therapists will encourage savoring of the experience and encourage facial expression of the positive emotions, so that clients do not dampen, avoid, or minimize the experience. This is particularly relevant with depression.

In **Session 2 (Unproductive Processing)**, therapists will describe in more depth the unproductive processing loop that can keep people locked in recurrent thinking and worrying as they try to make meaning of difficult life events. The therapist will describe how one can repetitively try to make sense of the event without updating meaning and overgeneralize across situations and beliefs about the self, others, and future, which can be overwhelming. In **Session 3 (Avoidance)**, avoidance will be described as the tendency to push away feelings, thoughts, memories, people, and situations to attempt to reduce distress.

Clients are taught that avoidance often backfires and is associated with intrusions, re-experiencing, and rumination. In **Session 4 (Reward Deficits)**, therapists will describe in depth how reward deficits can perpetuate distress and interfere with the benefits of positive emotion and reward processing.

Sessions 5 (Integration) focuses on constructive processing and provides opportunity for integration and consolidation of learning. **Session 6 (Future Events)** focuses on future negative and positive events to promote application of new learning and resilience. Booster sessions focus on positive and negative life events since the last session and adaptive processes (constructive processing, approach, and reward). All sessions will include cultivation and elaboration of positive emotions to promote engagement and to build on the benefits of positive emotion.

Progressive Muscle Relaxation (PMR). PMR is for the R33 as one of the randomization conditions and will be adapted from Bernstein, Borkoveck, and Hazlett-Stevens (2000). PMR will be conducted in six, 60-90 min individual weekly sessions with a study therapist, helping control for non-specific effects of contact time, treatment expectancy, and general support. This intervention is likely to be credible because of the focus on stress management, and it does not focus directly on the PATH targets. Muscle groups are tightened and then relaxed with the attention of the patient focused on the contrast between tension and relaxation. Through regular practice, the person becomes more aware of tension in the body and can induce relaxation as needed (Field, 2009). During the six sessions of training, patients will be encouraged to practice PMR and learn how to deliberately induce physical relaxation to reduce stress and mental tension. Sessions will move from relaxation of 16-muscle groups to 7 muscle groups, 4 muscle groups, and finally to relaxation by recall. Patients will be instructed to practice daily, if possible, but at least two or three times a week, and to integrate the practice into their daily life. Every session, patients will be provided with audio recordings of the PMR conducted that session with their therapists, as well as homework reporting forms to assist their home PMR exercises.

Study Timeline

Directions: State approximately how long each visit will take, how long total study enrollment will last.

	Year 1				Year 2				Year 3			
	Q1	Q2	Q3	Q4	Q1	Q2	Q3	Q4	Q1	Q2	Q3	Q4
PATH Pilot Study (Study 1)												
Procedures Finalized and Staff Trained					X							
Final IRB Approval and Material Prep					X							
Assessor and Therapist Training	X				X			X				
Recruit Participants	X	X	X	X	X	X	X	X				X
Patient Treatment		X	X	X	X	X	X	X				X
Assessment			X	X	X	X	X	X				X
DSMB Annual Report/Meeting					X							
25% Recruitment Target (n = 12)					X							
50% Recruitment Target (n = 22)						X						
75% Recruitment Target (n = 34)							X					
100% Recruitment Target (n = 45)								X				
Analyzing and Interpreting Results									X			X
Evaluation of Go/No-Go Rules										X		X
Manuscript Preparation and Submission										X		X
General Grant Procedures												
Research Performance Progress Reports					X				X			
Data Sharing NDCT					X				X			
Year 3				Year 4				Year 5				
Q1	Q2	Q3	Q4	Q1	Q2	Q3	Q4	Q1	Q2	Q3	Q4	
PATH RCT (Study 2)												
Refine PATH					X							
Procedures Finalized and Staff Trained					X							
Final IRB Approval and Material Prep					X							
Assessor and Therapist Training	X				X			X				X
Recruit Participants		X	X	X	X	X	X	X	X			X

Patient Treatment	X	X	X	X	X	X	X	X	X	X
Assessment	X	X	X	X	X	X	X	X	X	X
25% Recruitment Target (n = 34)			X							
50% Recruitment Target (n = 67)					X					
75% Recruitment Target (n = 101)							X			
100% Recruitment Target (n = 135)								X		
Analyzing and Interpreting Results									X	X
Manuscript Preparation and Submission									X	X
General Grant Procedures									X	X
Research Performance Progress Reports			X			X		X		X
Data Sharing NDCT	X		X		X		X		X	X

Phone Screening. Members of the study team will collect demographic data and complete an eligibility screening form (type of destabilizing event, inclusion/exclusion criteria). Brief versions of the PSS-I and QIDS-C will be used. Potentially eligible individuals will be scheduled for an intake; those excluded will be given referrals and we will retain their demographic information and reason for exclusion for the creation of consort diagrams. All clinical data will not be utilized and ultimately deleted.

Pre-treatment Assessment. After informed consent, a study team member (licensed therapist or under the supervision of someone licensed) will administer measures of PTSD (PSS-I), depression (QIDS-C), and suicidality (C-SSRS). Assessors will be blind to treatment assignment (in R33). Patients will complete baseline self-reports and laboratory paradigms. See Figure 2.

Active Treatment. Someone on the study team (licensed or under the supervision of someone licensed) will administer the treatment sessions. In the R61, all patients will receive PATH. In the R33, patients will be randomized to PATH or PMR, using a computerized algorithm accounting for initial symptom severity.

Post-Treatment Assessment. A study team member, either someone licensed or under the supervision of a licensed therapist, will re-administer PSS-I, QIDS-C, and C-SSRS; patients will complete self-reports and tasks of target engagement. Treatment dropouts will be immediately assessed and will stay in the assessment portion of the study.

Booster Sessions. Partial responders (less than 20% reduction on PTSD or MDD symptoms; Graham et al., 2017) to the 6 sessions of PATH or PMR will receive 2 booster sessions from members of the study team (licensed or under the supervision of someone licensed). All others will enter follow-up. This will provide **dosing and timing** information by examining how many participants respond to 6 sessions, and how many become responders with the booster sessions.

1- and 3-Month Follow-up Assessments. Patients will be re-evaluated 1 and 3 months after treatment by a member of the study team (licensed or under the supervision of someone licensed). The PSS-I, QIDS-C, and C-SSRS will be re-administered, and all self-reports and tasks of targets engagement will be completed. Additional treatment will be documented and referrals provided as needed.

Data to be Collected for your study (AFTER consent and HIPAA Authorization have been obtained)

List all data to be collected for the research study or attach a data collection sheet (e.g. laboratory values, physician notes, length of stay, etc.)

At the beginning of the intake, participants will complete the informed consent process prior to the collection of study data. After the informed consent process, information for the NIMH Data Archive GUID (full name, sex, date of birth, and city of birth) will be collected at baseline. More information about the GUID can be found in section 9 of the supplemental protocol. During intake, also after the informed consent process, a participant information and history interview, a destabilizing life event history interview, and a brief goal assessment interview will be conducted.

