Data will be screened for accuracy, missing values, and fit with the assumptions of GLMM (e.g., linearity, multivariate normality; Tabachnick & Fidell, 2007). Data transformations or model re-specifications will be performed, if needed. Outcome data will be plotted against time to guide selection of applicable time variables; similarly, covariance matrices will be examined to inform selection of the best covariance structure. Best fitting models will be evaluated based on these plots and model fit information (e.g., AIC, BIC). We will use pattern-mixture models to examine whether missingness can be considered ignorable. For non-ignorable missing data, values will be multiply imputed and data recombined (Rubin, 1987) in the mixed model program or comparable model-supported approaches. We will examine associations between primary dependent variables with factors such as gender and time since event and make appropriate adjustments (e.g., covarying predictors). In analyses nesting subjects within treatments (Aim 2), dummy codes will be used (Snijders, 2005).

Power Analysis

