Our approach to power analyses aims to balance pragmatic factors with analytic considerations. We focus primarily on Specific Aim 1 (R61) and Specific Aim 2 (R33). Primary analyses for both aims will involve random effects models; however, because it is difficult to accurately estimate covariance structures of such models, *a priori* power or sample size estimations have limited value. Fang (2006) has shown that ideal sample sizes often far exceed clinical resources for conventional trials, whereas other studies have shown that small sample sizes do not bias estimates of fixed effects (e.g., Bell et al., 2008). Accordingly, we frame our power calculations in line with GLM models that mirror the primary tests and hypotheses of our more complex random effects/GLMM models. In general, estimates were calculated based on $\alpha = .05$ and power $(1 - \beta) = .80$, using intent-to-treat, repeated-measures designs (e.g., paired t-tests). Power calculations were completed using G*Power (Faul et al., 2007). For Aim 1, with an estimated pre-post effect size of $d = 0.60$ (one-tailed tests), we are well-powered with a sample of 45. In fact, for a sample size of 45, an alpha of .05, and power of .80, we will be able to detect a small to moderate effect size of .38. For Aim 2, we based power estimates on a primary comparison of time by treatment interaction in an RMANOVA model. For a five time points, two groups, RMANOVA with a correlation of $r = .70$

between measures, we are well powered to detect treatment X time small effect size of .07 with 67 patients per treatment. For Specific Aim 3, using Monte Carlo simulations in MPlus 6.0 (Muthen & Muthen, 2002) with the same alpha, power, and sample size of at least 67 per condition, we are adequately powered to detect an indirect effect size as small as $d = .50$.

Specific Aim 1: Engage Targets (R61)

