We will create a Data Safety and Monitoring Board (DSMB). We will include experts in statistics, PTSD and depression psychotherapy and clinical trials. These individuals will be experts in their fields and not associated with the trial in any manner. The DSMB will review the research protocol and plans for data safety and monitoring. They will be responsible for evaluating the progress of the RCT including recruitment, retention, and ongoing risk benefit ratio. The DSMB will receive an annual report that reviews recruitment, randomization, preliminary results for intervention, and safety data. Masked data will be presented to the DSMB, with the PI and investigational team remaining blind to the ongoing trial results. Only members of the DSMB will see interim data. The DSMB will also consider factors external to the study, such as scientific or therapeutic developments that may have an impact on the safety of the participants or the ethics of the study. The DSMB will convene annually to review this report and provide written feedback for the PI on questions or concerns related to the trial that need to be addressed. The PI will respond within 24 hours to any serious concerns raised by the DSMB. Each year the DSMB will recommend continuation or stoppage of the trial.

Drs. [name], [name] and [name] will be responsible for data and safety monitoring and will provide continuous, close data monitoring at each site. [name] will follow UW's SAE reporting policy in promptly reporting serious adverse events to the UW Institutional Review Board (IRB) and to NIMH. [name] will follow CWRU/UHC SAE reporting policy in promptly reporting serious adverse events to the CWRU/UHC Institutional Review Board (IRB) and to NIMH. [name] will follow UD's SAE reporting policy in promptly reporting serious adverse events to the UD Institutional Review Board (IRB) and to NIMH. Drs. [name], [name] and [name] will report all SAEs to their respective IRBs within 24 hours. A report of all non-serious adverse events will be provided to the IRB yearly. NIMH will be informed of all actions taken by the IRB as part of its continuing review.

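### The R33 allocation and the Aim 2 model do not name site, although 135 patients come evenly from three sites: a modest, avoidable loss of precision

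*Combined protocol and SAP*

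**What the plan says.** - **Allocation.** The Active Treatment paragraph under Study Timeline says that R33 patients are randomised to PATH or PMR "using a computerized algorithm accounting for initial symptom severity". It states no other factor, and no ratio, block size or strata.
- **Sites.** Under Number of Research Participants: "This study is being conducted in collaboration with the University of Washington and the University of Delaware". With the local university that makes three sites, and "for the R33, 135 participants will be evenly accrued across all sites", or about 45 at each. The Setting section gives each site its own recruitment area in Ohio, Delaware or Washington.
- **Adjustment.** The General Analytic Strategy will look at how the primary dependent variables relate to "factors such as gender and time since event" and adjust as appropriate. Site is not mentioned.
- **Aim 2 model.** The equation under Specific Aim 2 contains time, treatment, their interaction, and a random intercept and slope for each subject. It is used both for the level at 3-month follow-up and for change over time. It has no site term.
- **Power.** The Aim 2 power paragraph does not mention site.

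**The concern.** Site is known before a patient is randomised, and it can plausibly carry differences in outcome. Recruitment areas differ. The Behavioral Approach Task, one of the three primary target measures, is built individually with each participant. The COVID-19 changes to data collection make evaluator assessments depend on each site's rules for in-person research.

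If the arms are uneven within sites, part of any difference between sites appears in the PATH versus PMR comparison as extra noise. Uneven splits also make it harder to check that an effect holds at all three sites. Target engagement in the R33 feeds the decision on a later R01 (Milestones), so precision here has a use. Allocation cannot be redone after enrolment, and a site adjustment chosen after seeing the data is easier to challenge than one written in advance.

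**Working it through.** **The plan's own Aim 2 figure.** The inputs from the Power Analysis section are two groups, five time points, r = .70, alpha .05, power .80, 67 per arm and a detectable effect of .07, taken here as Cohen's f. For the within-between interaction under sphericity, lambda = f² x N x m / (1 - r), with df = 4 and (134 - 2) x 4 = 528.
- At 80% power the detectable f is 0.0734: lambda = 0.0734² x 134 x 5 / 0.30 = 12.0. This rounds to the stated .07.
- At exactly f = .0700, lambda = 10.9 and power is 75.5%.

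The figure therefore reproduces to two decimals, and site has no part in it.

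**Within-site imbalance if site is ignored.** Inputs: 135 patients and three sites of 45. Assumption: 67 on PATH and 68 on PMR, because 67 per arm implies 1:1. The number on PATH at one site is then hypergeometric.
- Variance = 45 x (67/135) x (68/135) x (90/134) = 7.56, so SD = 2.75 patients. The 95% range is 17 to 28 of 45.
- Enumerating all three-site splits exactly gives the chance that at least one site is this uneven:

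| Split at some site | Probability |
|---|---|
| 26:19 or worse | 52% |
| 27:18 or worse | 31% |
| 28:17 or worse | 16% |
| 30:15 or worse | 3% |

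A simulation that blocks on severity alone (blocks of 4, two severity strata, severity independent of site; 20,000 trials) gives 53%, 32% and 16% for the first three rows. Balancing on severity does not protect site.

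**Effect on the arm difference.** Let one site differ from the other two by D, in SD units. The error in an unadjusted PATH minus PMR difference is D x (n_PATH/67 - n_PMR/68), where the counts are those at that site. Its mean is zero apart from rounding. Its SD is D x 2.75 x (1/67 + 1/68) = D x 2.75 x 0.02963 = 0.0814 D.

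The standard error of a 67 versus 68 comparison is sqrt(1/67 + 1/68) = 0.172 SD. Ignoring site multiplies it by sqrt(1 + (0.0814 D / 0.172)²).

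| Assumed D | Error SD | 97.5th percentile of error | Increase in standard error |
|---|---|---|---|
| 0.2 | 0.016 | 0.034 | 0.4% |
| 0.5 | 0.041 | 0.084 | 3% |
| 0.8 | 0.065 | 0.134 | 7% |

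The documents give no site differences, so D is an assumed range.

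**Which Aim 2 estimate is exposed.** A stable difference in level between sites enters every time point of a patient alike, so it largely cancels from the treatment x time slope. It does not cancel from the 3-month level estimate. A site difference in change over time does not cancel from either.

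**With site in the allocation.** In the same simulation, stratifying by site and severity cuts the mean largest within-site arm difference from 6.6 to 1.5 patients. No trial in 20,000 had a site differing by 7 or more. With three evenly spaced sites, the error SD per 1-SD gap between the extreme sites falls from 0.070 to 0.014.

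**The case against.** Four points on the other side carry weight.

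1. **The protocol does not say that severity is the sole factor.** A reader might infer that site is excluded from the algorithm. The text supports only that site is not named. The section on data to be collected also mentions a supplemental protocol, which is not among the documents. This stands: if site is already used, one added phrase settles the allocation half of the point.

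2. **Chance imbalance is not bias.** A reader might infer that site differences distort PATH versus PMR in a particular direction. Nothing in the documents supports that. The error averages zero and is small beside the ordinary standard error. This stands too, and it sets the size of the point.

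3. **A site term in the analysis does most of the work.** If site is ignored at allocation but fitted in the model, average efficiency is about 98.5% of perfect within-site balance, and about 96% at the 5th percentile. The efficiency is the sum over sites of n_PATH x n_PMR / 45, divided by its value under perfect balance. The open-ended adjustment clause would permit such a term. But it does not name site, and the choice would depend on the data.

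4. **The route by which site acts is partly inference.** A reader might suppose that each local team treats and tests only its own patients. The documents do not say so, nor how therapists are assigned to arms. The statement that site leads "will provide continuous, close data monitoring at each site" concerns data and safety monitoring, not treatment delivery. Procedures are remote for the foreseeable future, and two of the three primary tasks are run online, which leaves less room for local effects.

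A reader might also expect some site to be left with very few patients in one arm. The enumeration makes that rare: an arm of 15 or fewer at some site in about 3% of trials, and of 13 or fewer in about 0.3%.

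**Conclusion.** The point holds as a gap in specification with a modest cost in precision. Site is not named in the R33 allocation, in the adjustment examples or in the Aim 2 model, although equal recruitment at three sites is planned. If allocation does ignore site, a split of 26:19 or worse somewhere is about as likely as not.

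The price ranges from negligible at a 0.2 SD site gap to about 7% in standard error at 0.8 SD. It falls on the 3-month level estimate and on site differences in change, more than on stable differences in level. The sizes rest on 45 patients per site, 1:1 allocation and the assumed gaps. The point does not threaten the validity of the randomised comparison. It is worth acting on because the protection is standard and nearly free before the R33 opens.

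**What to change.** - **Active Treatment (Study Timeline).** State that the computerised algorithm accounts for site as well as initial symptom severity. This can be done with blocks of varying size within site-by-severity strata, or with site as a minimisation factor.
- **Specific Aim 2 (Data Analysis Plan).** Prespecify site and site x time as fixed terms in the Aim 2 models. Site main effects alone adjust for level but not for site differences in change.

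**Cost.** With three sites and linear time the model spends 2 + 2 = 4 degrees of freedom. If the five time points are categorical it spends 2 + (2 x 4) = 10. The allocation becomes slightly more complex to set up. Sample size, visits and treatments are unchanged.
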